5.1.5 Data and Safety Monitoring Committee (DSMB)

The study will have a DSMB composed of a physician chairman/chairwoman, three member physicians and a DSMB statistician all of which may vote. At least one physician should be an Infectious Disease or rabies expert. The voting members will not be directly involved with the conduct of the study. Voting members will not be employees of the sponsor. Additional non-voting subject area experts may be present at meeting to provide expertise if requested by the DSMB. The DSMB will operate according to its charter.

The DSMB will have five responsibilities

1. Review of Study Drug pharmacodynamic activity in the Initial Enrollment of the LRG subjects and granting permission for general LRG enrollment (5.1.5.2).
2. Review of safety and pharmacodynamics through Study Day 99 in the initial and general enrollment groups of the LRG (5.1.5.3)
3. Review of Study Drug safety after 80 subjects have reached Study Day 9 (5.1.5.4)
4. Review and confirmation of any possible rabies cases in trial participants.
5. Management of safety issues during the trial.

The DSMB will not determine exclusions from the per protocol population. Exclusions from the per protocol population are determined by the Per Protocol Adjudication Board. The DSMB may request review of any case by this board.

5.1.5.1 DSMB Confirmation of Rabies Cases in the Trial

A confirmed or probable case of rabies is an element of the composite endpoint for the trial (Section 3.9.1). If a case of rabies occurs in the SYN023 treatment group of the per protocol population in the trial it will result in the failure of the primary objective and the cessation of Study Drug administration in the trial. The DSMB will review and confirm a rabies diagnosis in any study participant and determine if trial enrollment or Study Drug administration should be stopped. The DSMB may require additional subjects in the Initial Enrollment.

5.1.5.2 DSMB Evaluation of Safety and Pharmacodynamic Activity in the Initial Enrollment LRG

The sponsor will collect blinded RVNA results and adverse events through Study Day 29 from the subjects in the LRG initial enrollment group and provide this information to the DSMB. Permission to enroll the General Enrollment of the LRG may be granted if

- no protocol stopping rules are met (Section 6.3) and if
- no severe related adverse events other than local injection site manifestations are encountered due to SYN023 in the initial enrollment of the LRG
- the serum RVNA values are all in the protective range (≥ 0.5 IU/mL Section 3.9.2) on Study Days, 8 through 29 in the SYN023 recipients.

The DSMB will issue a written determination permitting enrollment of the general enrollment group of the LRG and inform the sponsor of this determination. It is acknowledged that some HRIG recipients may not have achieved ≥ 0.5 IU/mL RVNA by Study Day 8.

5.1.5.3 DSMB Review of Safety and Pharmacodynamic Activity in the Initial and General Enrollment LRG

The sponsor will collect blinded RVNA results and adverse events through Study Day 99 from all subjects in the LRG General and Initial enrollment groups and provide them to the DSMB. Permission to enroll the General Enrollment of the NRG may be granted at Study Day 183 if

- no protocol stopping rules are met (Section 6.3) and if
- no severe related adverse events other than local injection site manifestations are encountered due to SYN023 in the initial and general enrollment of the LRG
- The RVNA values are in the protective range in $\geq 75\%$ of SYN023 recipients on Study Day 99 (Section 3.9.2).

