2.4 Study Duration and Follow-up

Subjects will be followed for 365 days post receipt of Study Drug unless withdrawn from the trial. It is important to have follow-up information on all study enrollees for the full duration of the study. Every effort should be made to remain in contact with study subjects in at least six-week intervals to establish if the subject is in good health and to inquire about planned relocations. If health problems have occurred a verbal or written account of the duration and character of the difficulties should be obtained. This is specially important in the last six months of the study when clinic visits are less frequent.

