3 STUDY PROCEDURES

3.1 Schedule of Subject Evaluations

A Summary Schedule of Evaluations depicting all visit-specific procedures is provided in Table 3-1. A more detailed description of the tasks and evaluations by Study Day is supplied in the Appendix. A table of phlebotomy volumes by visit may be found in Appendix C.

Table 3-1 Summary Schedule of Subject Evaluations LRG Group

Study Visit Day →	1	4	8	15	29	43	71	99	127	155	183	274	365
Visit window (days)	0	0	0	0	2	4	7	7	7	7	14	14	14
Written informed consent	X												
Eligibility criteria verification	X												
Medical history	X												
Physical examination	X												
ECG	X												
Urine βHCG (all females)	X												
Hepatitis B, C ^a	4												
HIV ^a	5												5
CBC, platelets ^a	2	2		2		2							
Urinalysis ^a	X												
Serum chemistry ^{a, c}	4	4		4		4							
PT(INR), PTT ^a	2					2							
Bite wound washing	X												
Vital signs	X	X	X										
Interval history		X	X	X	X	X	X	X	X	X	X	X	X
Focused physical examination		X	X	X	X	X	X	X	X	X	X	X	X
Wound photographs	X												
Randomization	X												
Study Drug Wound Injection	X												
Rabies Vaccination	X	X	X	X	X								
Serum RVNA	10 ^a	10 ^b	10 ^b	10 ^b	10 ^b	10	10	10	10	10	10	10	10
Confirmation visit	X	X	X										
Anti-SYN023 serum assay	5 ^a			5	5			5					
SYN023 concentration	5 ^a	5 ^b	5 ^b	5 ^b	5 ^b	5		5					
Adverse events (incl. con. Meds.)	X	X	X	X	X	X							
Solicited adverse events	X	X	X										
Serious adverse events (incl. con. Meds.)	X	X	X	X	X	X	X	X	X	X	X	X	X
Site of injection examination	X	X	X	X	X								
Per visit phlebotomy volume	37	21	15	26	20	23	10	20	10	10	10	10	15
Cumulative phlebotomy volume	37	58	73	99	119	142	152	172	182	192	202	212	227

- a. Study Day 1 samples must be obtained before Study Drug administration
- b. Samples must be obtained before vaccination.
- c. Serum chemistries are total bilirubin, AST, ALT, ALP, creatinine, blood urea nitrogen, sodium, potassium, chloride, bicarbonate, calcium.
- d. Numbers in lab specimen rows indicate **approximate** blood volume in mL.

Table 3-2 Summary Schedule of Subject Evaluations NRG Group

Study Visit Day →	1	4	8	15	29	43	71	99	127	155	183	274	365
Visit window (days)	0	0	0	0	2	4	7	7	7	7	14	14	14
Written informed consent	X												
Eligibility criteria verification	X												
Medical history	X												
Physical examination	X												
ECG	X												
Urine βHCG (all females)	X												
Hepatitis B, C ^a	4												

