3.12 Safety Evaluations

3.12.1 Adverse Event Reporting Intervals

The collection periods for adverse events are:

Unsolicited adverse events: Through Study Day 43

Solicited adverse events: Through Study Day 8

Serious adverse events: Entire study period (i.e., 365 days)

For this study, solicited adverse events to be collected are listed in section 5.7 Solicited Adverse Events.

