The reporting period for all adverse events is specified in Section 3.12.1. Adverse events will be reported on the Adverse Event CRF using a recognized medical term or diagnosis that accurately reflects the event. Adverse event evaluations will be reviewed by the principal investigator or by a designated medically qualified practitioner. Adverse event CRF pages are to be completed by members of the study team designated in writing by the principal investigator. The onset and resolution dates of the event and action taken in response to the event will be documented. All adverse events must be followed until resolution is demonstrated. The resolution date will be recorded on the CRF as the last date on which the subject experienced the adverse event. If an adverse event resolution date is uncertain the principal investigator should estimate the completion date based on medical judgment and interview of the subject. Approximate dates of resolution from interviews may be taken as adverse event resolution dates. Some examples of estimation of adverse event resolution are: 1) an asymptomatic laboratory abnormality on one visit that has not been followed-up between visits but has resolved by the next visit may be assumed to have resolved by the midpoint of the inter-visit interval; 2) A resolved adverse event that was treated may be assumed to have been resolved by the end of treatment. Adverse events that are still present at the end of the trial should be recorded as ongoing. Information recorded on the CRF must be substantiated in the source documents. If an adverse event evolves into a condition that becomes “serious,” it will be designated as serious on the Adverse Event CRF and a Supplemental SAE Report (SAER) form will be completed.

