5.4 Assessing Severity

The safety concepts of “severity” and “seriousness” are distinct concepts (see Section 5.8). Severity refers to a degree of clinical manifestation. “Seriousness” refers to defined outcomes from an adverse event. A severe adverse event is not always serious and a serious adverse event is not always severe.

For all adverse events, the investigator (or designee, who is a healthcare professional; is someone the investigator deems qualified to review adverse event information, to provide a medical evaluation of the event, and to classify the event based upon medical judgment and the severity categories described below) is responsible for assessing the severity of the event and the causal relationship of the event to the Study Drug.

The **severity** of all adverse events, including clinical findings and abnormal laboratory values, will be classified as one of the following grades:

1. **Mild**
2. **Moderate**
3. **Severe**

A Toxicity Table is provided in the protocol appendices for the assessment of severity of specified adverse events. The Toxicity Table Adverse Event Grades do not correlate directly with the classical severity grades of mild, moderate and severe. FOR THE PURPOSES OF RECORDING EVENTS ON THE CRF, Toxicity Table Grade 1 events will be considered mild in severity, Toxicity Table Grade 2 events will be considered moderate in severity, and both Toxicity Table Grade 3 and 4 events will be considered as severe. In the Toxicity Table certain local reactions such as erythema (redness) and swelling are graded according to size. Laboratory values are graded according to level of deviation from the normal range.

For adverse events not listed in the Toxicity Table determination of severity requires some level of interpretation as outlined below. The degree of incapacity caused by the adverse event and the level of medical intervention required for treatment may be helpful in assessing the overall severity of the adverse event.

For example:

- “Mild” events are generally regarded as noticeable but have no impact on normal activities; they may or may not require over-the-counter treatment managed by the subject.
- “Moderate” events generally have some impact on an individual’s normal activities and may require general symptomatic medical intervention by a healthcare professional or by the subject.

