9.1. Adverse Events

The primary variable for evaluation of the safety profile will be the number and percentage of AEs recorded after study drug administration. For selected of AE tables, additional summaries based on reporting period of adverse events following each vaccination (RabAvert® or Rabipur®) will also be presented.

The collection periods for adverse events are:

- Solicited AEs: Through Study Day 8
- Unsolicited AEs: (After Study Day 8) Through Study Day 43
- SAEs: Entire study period (i.e., 365 days)

All AEs will be classified by SOC and PT according to MedDRA, Version 21.0 or later. Summaries of the total number of treatment-emergent AEs (TEAEs) and the number and percentage of subjects with at least one TEAE will be provided by treatment. TEAEs will be presented by SOC and PT. At each level of subject summarization, a subject is counted once if the subject reported one or more events. Percentages will be calculated out of the number of subjects in the As-treated Population.

The summary of TEAEs will be presented in alphabetical order of SOC. Within each SOC, PTs will be sorted in descending order from the PT with the highest total frequency (that is, summed across all treatment groups) to the PT with the lowest total frequency. If the total frequency for any two or more PTs is equal, the PTs will be presented in alphabetical order.

SAEs will be recorded through the final study visit for all subjects. Listings will be provided for subjects with SAEs. Listings will also be provided for subjects who have discontinued prematurely due to an AE.

All AE summaries will be restricted to TEAEs only. A TEAE is defined as any event not present before exposure to study drug or any event already present that worsens in either intensity or frequency after exposure to study drug.

For inclusion in TEAE tables, incomplete AE start and end dates will be imputed following rules specified in Section 15.3.1.

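### The gate into the Normal Risk Group relies on severe related adverse events through Study Day 99, but the recording rules for non-serious events stop at Study Day 43 (minor)

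*Protocol*

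**What the plan says.** Protocol 5.1.5.3 describes the data behind the decision to open the NRG: "The sponsor will collect blinded RVNA results and adverse events through Study Day 99 from all subjects" in the initial and general LRG enrollment. Among its conditions for permission is this one, applied to the whole LRG: "no severe related adverse events other than local injection site manifestations are encountered due to SYN023 in the initial and general enrollment". The test is severity plus relatedness. It is not limited to serious events, and Protocol 5.4 keeps the two ideas apart: "A severe adverse event is not always serious and a serious adverse event is not always severe".

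The recording rules use a shorter window:
- Protocol 3.12.1: "Unsolicited adverse events: Through Study Day 43". Solicited events end at Day 8. Only serious adverse events (SAEs) run for 365 days.
- Protocol 5.3: "The reporting period for all adverse events is specified in Section 3.12.1".
- Protocol Table 3-1 (LRG): the row "Adverse events (incl. con. Meds" is marked at Days 1, 4, 8, 15, 29 and 43 and at no later visit.
- Protocol Appendix D: for LRG Days 71 and 99 the only adverse event task is to record SAEs.
- SAP 9.1: "Unsolicited AEs: (After Study Day 8) Through Study Day 43". In the LRG schedule of SAP 15.1.1, footnote m restricts the visits from Day 71 onward to SAEs.

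**The concern.** A safety gate should be testable from the data the plan collects. Here the gate names a window that ends at Day 99, while a site following its visit schedule stops entering non-serious adverse events at Day 43. For the days in between, the condition on severe related events could be judged met because an event was not entered, and not because none occurred. The gate matters: it opens SYN023 to head, neck, genital, arm and hand bites (Protocol Table 2.2-1), which the LRG excludes as the exposures of highest rabies risk.

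**Working it through.** The plan states no figure to reproduce. The check compares the gate with each route by which a late event could be recorded.

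**Span.** Gate window to Day 99; recording of non-serious events to Day 43. 99 − 43 = 56 days (Days 44 to 99), and 56/99 = 57% of the window. The LRG has 80 subjects, of whom up to 15 + 30 = 45 receive SYN023 (Protocol Table 2.3-1). The earlier gate in 5.1.5.2 is unaffected, because its Day 29 cut lies inside the 43-day period.

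**What is covered after Day 43.**
- Severe events that are also serious: SAEs to Day 365 (3.12.1, 5.8).
- Events with onset by Day 43 that persist or worsen: followed up, with the highest grade recorded (5.4, 5.13).
- Suspected allergic reactions: immediately reportable, with no end day (5.12).
- SUSARs, related SAEs and patterns of grave concern: pausing rules that apply at any time (6, 6.2).

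**What remains.** A new event on Days 44 to 99 that is severe and related, but non-serious, non-allergic and not local. The class is not empty. A headache treated with a narcotic pain reliever is Grade 3 (Appendix B), and Grade 3 is coded as severe (5.4). That alone meets no seriousness criterion in 5.8. An emergency room visit counts as hospitalization there only beyond 24 hours. Headache was the most common related event in earlier studies (1.4), though no onset time or severity is given.

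**Does another rule put such an event on the AE CRF?**
- Detection is likely enough. There is an interval history and focused examination at each visit (Table 3-1), a symptom question at every clinical contact (3.12.2), self-report (3.12.5), and contact at least every six weeks, where "If health problems have occurred a verbal or written account of the duration and character of the difficulties should be obtained" (2.4). None of these asks for an AE CRF entry after Day 43.
- Assessment is required. Sections 5.1.1, 5.3, 5.4 and 5.5 have the investigator judge severity and causality for every adverse event, with no end day. But 5.3 ties reporting to the period in 3.12.1.
- Concomitant medication is an ambiguous route. Section 3.12.4 requires each indication to match an AE CRF term, a pre-existing condition or prophylaxis, and Appendix D lists medication recording at Days 71 and 99. The same section ends collection of medication for non-serious events 42 days after Study Drug.

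**Drug exposure in the span.** Protocol 1.6 puts Day 121 at over 5 half-lives. Day 121 is 120 days after dosing, so the half-life is below 120/5 = 24 days. Assuming first-order elimination and ignoring absorption time:
- Day 44: below 2^(−43/24) = 0.289 of the dose.
- Day 99: below 2^(−98/24) = 0.059 of the dose.

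These are upper bounds. The same paragraph of the protocol states that SYN023 is not detectable in blood by Day 99.

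**Illustration on assumed rates only.** The chance of at least one such event among 45 recipients is 1 − (1 − p)^45: 4% at p = 0.1%, 20% at 0.5%, 36% at 1%, 60% at 2%. The documents do not say where in this range, or outside it, the true rate lies.

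**The case against.** The strongest reply is that 5.1.5.3 is itself a collection instruction: it says the sponsor will collect adverse events through Day 99 from LRG subjects, so it can be read as extending the general window for this group. That reading is fair, and it makes the problem a conflict between sections more than a plain omission. It does not remove the problem, because no visit schedule, reporting rule or SAP section carries the extension out, and 5.3 sends the reader to 3.12.1.

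A second reply also stands. A reader might infer that late severe events go ungraded and without a causality judgment. The documents do not support that: the duty to assess covers every adverse event and has no end day. What is missing is a scheduled place to record the result and pass it on.

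Third, the Day 43 limit fits the pharmacology. Protocol 1.4 gives 35 to 42 days of supra-inhibitory levels at the study dose, so late related events should be uncommon. This bears on the size of the gap, not on whether the sections agree.

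Fourth, a separate DSMB charter (Protocol 5.1.5, SAP 13) may ask for more. It is not among the documents, so it cannot be relied on to close the gap.

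**Conclusion.** The inconsistency is real and the point is minor. For one narrow class of late events, the gate's safety condition rests on a record that no schedule or reporting rule calls for. Such an event need not reach the DSMB as a recorded adverse event; it would be too strong to say that it cannot.

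A reader might also infer that the DSMB has no safety data after Day 43, or that the NRG would open without safety oversight. Neither follows, given SAE reporting to Day 365, the immediate-report rule and the pausing rules.

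The span of 56 days measures time, not risk. The judgment that the effect is small rests on low residual exposure, on the stated absence of detectable SYN023 by Day 99, and on how much else is covered. No event rate is available to confirm it.

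**What to change.** Preferred: in Protocol 3.12.1, Table 3-1 and Appendix D (LRG Days 71 and 99), and in SAP 9.1 and 15.1.1, require severe (Grade 3 or above) adverse events to be entered on the AE CRF with causality through Study Day 99 for LRG subjects. The cost is a protocol amendment, a SAP edit and one added check at two existing visits: 80 × 2 = 160 visits, up to 45 × 2 = 90 of them in SYN023 recipients. A CRF entry is needed only when a severe event is found. Late laboratory abnormalities would still go unseen, because scheduled chemistry, hematology and coagulation tests end at Day 43.

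If LRG follow-up is already past that point, restate 5.1.5.3 and item 2 of 5.1.5 as all adverse events through Study Day 43 and serious adverse events through Study Day 99. This costs only wording, but it leaves a weaker stated gate.

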5.1.5.4 DSMB Review of Safety in the NRG

The DSMB will assess the safety (while enrollment continues) after 80 subjects have completed Study Day 99. If there are no adverse events or patterns of concern it will issue permission for the trial to continue.

5.1.5.5 DSMB Management of Safety Issues in the Trial

If Study Drug administration is paused (see safety pausing rules in Section 6.1) by the principal investigator, the local medical monitor, or the global medical monitor, the DSMB will be convened. The DSMB may review an individual SAE or it may choose to review adverse events, serious adverse events, solicited adverse events, and laboratory and vital signs data. The DSMB may request unblinding any amount of safety information needed to conduct its safety assessment. Only the DSMB and the independent statistician responsible for preparing these analyses would be unblinded during these reviews. All procedures associated with this review, including objectives, data handling, and elements to be included for review will be documented in DSMB minutes.

Based on its review and the protocol stopping rules (Section 6) the DSMB will make recommendations in the DSMB minutes to the sponsor regarding further conduct of the study, changes to the study protocol and further administration of Study Drugs. The conclusions of the DSMB will be communicated to the investigators and the Institutional Review Boards/Ethics Committees and the national regulatory authority. The sponsor agrees to abide by the decision of its DSMB and any directives issued by the national regulatory authority, the Institutional Review Board or Ethics Committee.

If Study Drug administration is paused by the medical monitor or the global medical monitor, the DSMB will be convened. Based on its review and the protocol stopping rules (Section 6) the DSMB will make recommendations in the DSMB minutes to the sponsor regarding further conduct of the study and further administration of Study Drug. The DSMB may review an individual SAE or it may choose to review adverse events, serious adverse events, solicited adverse events, and laboratory and vital signs data. The DSMB may unblind any amount of safety information needed to conduct their assessment. All procedures associated with this review, including objectives, data handling, and elements to be included for review will be documented in DSMB minutes. The conclusions of the DSMB will be communicated to the investigators and the IRB/Ethical Committees and the national regulatory authorities. The

sponsor agrees to abide by the decision of its DSMB and any directives issued by the national regulatory authorities, the Institutional Review Boards or Ethics Committees.

